#### 4.6. PHARMACOKINETIC ANALYSIS SET [PKS]

The PKS will include all patients who receive at least one dose of study drug, have at least one measured drug serum concentration at a scheduled time point post-dose, and have no major protocol deviations or violations thought to significantly affect the PK of the drug (see section **Error! Reference source not found.**).

Patients in the PKS will be analyzed according to the treatment received.

#### 4.7. PHARMACODYNAMIC ANALYSIS SET [PDS]

The PDS will include all patients who receive at least one dose of study drug, have at least one measured PD variables (CD19+ B cell count) at a scheduled time point post-dose, and have no major protocol deviations or violations thought to significantly affect the PD of the drug (see section **Error! Reference source not found.**).

Patients in the PDS will be analyzed according to the treatment received.

#### 4.8. PROTOCOL DEVIATIONS

Criteria defining protocol deviations are referenced in the Protocol Deviation Guidance and Protocol Deviation Specification. The Protocol Deviation specification will be developed according to the guidance and updated whenever a new version of the guidance is released. Additional updates before unblinding may be added in the case of protocol deviations which are not specified in the guidance but are reported from sites and classified as critical/major following assessment

All Critical/Major protocol deviations captured by programming or reported protocol deviations from sites, will be transferred to the biostatistics (BIOS) group by the project manager in IQVIA via email, will be summarized by category of deviation (e.g. Inclusion criteria) and treatment group using the RAN; and all protocol deviations, minor and major, will be listed (indicating which deviations are minor and which are major).

Protocol deviations do not lead to patient withdrawal unless they indicate a significant risk to the patient's safety. Protocol deviations leading to patient exclusion from the specific analysis sets (except for PK set and PD set) will be determined based on blinded data review prior to database lock.

---

Document:

Author:

Version Number:

Version Date:

Final v1.0

10Sep2019

Template No: CS\_TP\_BS016 Revision 4

Effective Date: 01Apr2016

Reference: CS\_WI\_BS005

#### **4.8.1. DEVIATIONS RELATED TO PHARMACOKINETIC AND PHARMACODYNAMIC ANALYSIS**

Changes to procedures or events, which impact the quality of the PK and PD data, will be considered significant protocol deviations/events for the PK/PD analysis and will be described within the CSR body text. These changes or events will include any circumstances that could alter the evaluation of the PK and PD. Examples include, but may not be limited to, sample processing errors that lead to inaccurate bioanalytical results, and/or inaccurate dosing on the day of PK and PD sampling. In the case of a significant protocol deviation or event, PK and PD data collected during the affected treatment period will be excluded from the study results but will be included in the by-patient listings. Other changes to the procedures or events which do not impact the quality of the PK data will not be considered significant protocol deviations. A common example of a non-significant protocol deviation is deviations from blood sample collection times.

Deviations will be reviewed in a blinded manner prior to database lock. Based on this review, patients or PK/PD data points will be excluded from the analyses as deemed appropriate. Deviations or events with the potential to affect PK/PD results will be listed, as will the excluded data points.

### **5. General Considerations**

All patients will be tabulated according to their initial treatment group regardless of any dose adjustment during study conduct.

#### **5.1. STUDY DAY**

Study Day in days will be calculated from the date of the first study drug administration (Day 1) and will be used to show the start/stop day of assessment or event.

If the date of the event is on or after the first study drug date then:

- Study Day = date of event – first study drug date + 1.

If the date of the event is prior to the first study drug date, then:

- Study Day = date of event – first study drug date.

In the situation where the event date is partial or missing, the date will appear partial or

---

Document:

Author:

Version Number:

Version Date:

Final v1.0

10Sep2019

Template No: CS\_TP\_BS016 Revision 4

Effective Date: 01Apr2016

Reference: CS\_WI\_BS005

missing in the listings and Study Day will be calculated after proper imputation has been carried out as described in APPENDIX 1.

## 5.2. BASELINE

Unless otherwise specified, baseline is defined as the last non-missing measurement taken prior to first study drug date after informed consent is obtained (including unscheduled assessments). In the case where the last non-missing measurement and the reference start date coincide, that measurement will be considered pre-reference, but AEs and medications commencing on the reference start date will be considered post-reference.

Baseline for PD is defined as the value of CD19+ B-cell count, IgG, and IgM level at pre-dose on Day 1.

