5.2.3 Vital Signs

Vital signs will be assessed at the visits indicated in Table 1. Measurements will include systolic and diastolic blood pressure, pulse, respiratory rate, and oral or tympanic body temperature, and should be performed after the patient has been in a sitting/lying down position for at least 5 minutes.

During all infusions of the study drug, vital signs will be assessed at the following times:

1. Pre-infusion (within 10 minutes prior to the start of the infusion).
2. Start of infusion (within 30 minutes after the start of the infusion).
3. End of infusion (within 10 minutes after the end of the infusion).

Additional readings may be assessed at the discretion of the Investigator in the event of an infusion-related reaction.

The Investigator must assess all vital signs findings at each visit. If the Investigator finds any clinically relevant abnormalities, these should be reported as AEs/SAEs as appropriate.

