## **17.5. VITAL SIGNS**

The following vital signs measurements will be reported for this study:

- Systolic blood pressure (mmHg)
- Diastolic blood pressure (mmHg)
- Pulse (beats/min)
- Body Temperature (°C)
- Respiratory Rate (breaths/min)

---

Document:

Author:

Version Number:

Version Date:

Final v1.0

10Sep2019

Template No: CS\_TP\_BS016 Revision 4

Effective Date: 01Apr2016

Reference: CS\_WI\_BS005

- Weight (kg)

The following summaries will be provided for vital signs and weight data:

- Actual and change from baseline by visit and time point
- Shift table of incidence of significant abnormal values (low, normal, high), based on the criteria listed as below, from baseline to each post-baseline visit.
- Abnormalities by visit and overall abnormalities incidence result will be summarized and presented for all parameters, and further broken down by high/low abnormalities. Patients will be counted at most once for a high or low abnormality for each vital sign parameter.
  - Overall abnormal: Patient with at least one abnormal (abnormal high or abnormal low) result in post-baseline visit regardless of the baseline result.
  - Overall normal: Patient without any abnormal result in all post-baseline visits regardless of the baseline result.

A Listing of vital signs will be provided with results meeting clinically significant abnormal criteria marked as High (H) or Low (L)

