**Table 3 : Clinically Significant Abnormal Criteria of Vital Signs**

Variable	Unit	Visit	Low	High
Systolic	mmHg	Baseline	< 90 mmHg	> 180 mmHg

Document:

Author:

Version Number:

Version Date:

Final v1.0

10Sep2019

Template No: CS\_TP\_BS016 Revision 4

Effective Date: 01Apr2016

Reference: CS\_WI\_BS005

blood pressure		Post-baseline	≤ 90 mmHg AND change from baseline ≤ -20 mmHg	≥ 180 mmHg AND change from baseline ≥ 20 mmHg
Diastolic blood pressure	mmHg	Baseline	< 50 mmHg	> 110 mmHg
		Post-baseline	≤ 50 mmHg AND change from baseline ≤ -15 mmHg	≥ 105 mmHg AND change from baseline ≥ 15 mmHg
Pulse	beats/min	Baseline	< 50 beats/min	> 120 beats/min
		Post-baseline	≤ 50 beats/min AND change from baseline ≤ -15 beats/min	≥ 120 beats/min AND change from baseline ≥ 15 beats/min
Body temperature	°C	Baseline	< 35.0 °C	> 38.3 °C
		Post-baseline	≤ 35.0 °C AND change from baseline ≤ -1.1 °C	≥ 38.3 °C AND change from baseline ≥ 1.1 °C
Respiratory rate	breaths/min	Baseline	≤ 10 breaths/min	≥ 24 breaths/min
		Post-baseline	≤ 10 breaths/min	≥ 24 breaths/min
Weight	kg	Baseline	None	None
		Post-baseline	percentage change from baseline ≤ -7.0 %	percentage change from baseline ≥ 7.0 %

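### Read literally, the same-day rule in SAP 5.2 makes the Day 1 end-of-infusion reading the vital-sign baseline

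*SAP*

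**What the plan says.** - **General rule, SAP 5.2.** The default wording is: "baseline is defined as the last non-missing measurement taken prior to first study drug date after informed consent is obtained (including unscheduled assessments").
- **Same-day rule, SAP 5.2.** "In the case where the last non-missing measurement and the reference start date coincide, that measurement will be considered pre-reference". The rest of that sentence puts adverse events and medications that begin on the same date on the post-reference side. The term reference start date is not defined.
- **Only exception, SAP 5.2.** "Baseline for PD is defined as the value of CD19+ B-cell count, IgG, and IgM level at pre-dose on Day 1".
- **Vital-sign schedule, Protocol 5.2.3.** There are three readings at every infusion: first "Pre-infusion (within 10 minutes prior to the start of the infusion"), then "Start of infusion (within 30 minutes after the start of the infusion") and last "End of infusion (within 10 minutes after the end of the infusion"). The investigator may take further readings if there is an infusion-related reaction.
- **Outputs, SAP 17.5.** "Actual and change from baseline by visit and time point", together with shift tables from baseline to each post-baseline visit and counts of abnormalities. No separate vital-sign baseline is given.
- **Flags, SAP Table 3.** Baseline and post-baseline have separate rows. The post-baseline systolic Low criterion is "≤ 90 mmHg AND change from baseline ≤ -20 mmHg". The baseline Low criterion is a value below 90 mmHg with no change condition. Diastolic pressure, pulse and temperature have the same structure. Respiratory rate has no change condition in either row.
- **Protocol 8.5.** Baseline is in general the latest value before randomization, and detailed definitions for particular assessments are left to the SAP.

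**The concern.** A baseline should precede exposure. The same-day rule asks only whether the dates match, so it cannot tell a reading taken before the infusion from one taken after the full first dose. Vital signs are the assessment for which this matters.

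Infusion reactions are adverse events of special interest (Protocol 6.4). Protocol 6.4.6 says that severe ones typically occur at the first infusion, and it lists hypotension and fever among their signs. If the end-of-infusion value is baseline, the change-from-baseline tables cannot show a first-infusion effect at that time point, and every later visit is compared with a value that the drug may already have moved.

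The SAP is also uneven here. A hypotension event that starts during the first infusion is treatment-emergent, because SAP Appendix 1 compares date and time. The blood pressure recorded at the end of that same infusion would be pre-reference.

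**Working it through.** No figure in the plan has to be reproduced. The check applies the written rule to the schedule.

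**1. Which Day 1 assessments can be post-dose?**
- Safety laboratory tests are drawn before dosing on dosing days (Protocol 4.9; Table 1, footnote q).
- No ECG is scheduled on Day 1 (Protocol Table 1).
- PD variables have their own pre-dose baseline.
- Vital signs have two scheduled readings after the infusion starts.

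The practical effect is therefore on vital signs.

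**2. Which reading does SAP 5.2 select?** The first sentence alone selects a value dated before Day 1, such as screening. The same-day sentence selects the last non-missing value on Day 1, which is the end-of-infusion reading or a later extra reading, since unscheduled assessments count. As worded, neither sentence selects the pre-infusion reading when all three are present.

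**3. Worked case.** The systolic values (mmHg) are assumed for illustration and are not from the documents. Change = value − baseline.

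| Reading | Value | Change from 88 (literal rule) | Change from 120 (pre-infusion) |
|---|---|---|---|
| Day 1 pre-infusion | 120 | +32 | 0 |
| Day 1 start | 112 | +24 | -8 |
| Day 1 end | 88 | 0; Low at baseline (88 < 90) | -32; Low post-baseline |
| Day 8 pre-infusion | 120 | +32 | 0 |
| Day 8 end | 90 | +2; no flag | -30; Low post-baseline |
| Week 5 | 118 | +30 | -2 |

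Under the literal rule the Day 1 fall moves from the post-baseline row of Table 3 to the baseline row, and the Day 8 fall loses its flag.

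**4. Range of falls.** Pre-infusion value 120, end-of-infusion value 120 − d. Under the literal rule the Day 1 end change is (120 − d) − (120 − d) = 0 for every d.

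| Fall d | End value | Pre-infusion baseline | Literal rule |
|---|---|---|---|
| 0, 10, 20 | 120, 110, 100 | no flag | no flag |
| 30 | 90 | Low post-baseline (90 ≤ 90; -30 ≤ -20) | no flag: 90 is not below 90, and the change is 0 |
| 40 | 80 | Low post-baseline (80 ≤ 90; -40 ≤ -20) | Low at baseline |

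The row for a fall of 30 differs because the baseline threshold is strict (< 90) and the post-baseline threshold is not (≤ 90).

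**The case against.** The best defence is that nobody would program it this way. The governing sentence of SAP 5.2 asks for a value from before the first-dose date. SAP 17.5 reports by time point, which makes little sense if two of the three Day 1 readings precede baseline. A careful programmer would probably take the pre-infusion value. That may well be so, but no other section overrides the same-day sentence for vital signs, and the choice should not rest on the programmer.

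Several stronger inferences are tempting, and the documents do not support them:

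- **That infusion reactions are hidden.** They are not. Actual values are summarized by visit and time point, and all vital signs are listed (SAP 17.5). Clinically relevant findings are reported as adverse events (Protocol 5.2.3). SAP 17.1 summarizes infusion-reaction events and related events that start on the infusion day or the day after.
- **That a value of 88 goes unflagged.** It does not. The baseline row of Table 3 marks it Low, so the error is one of classification.
- **That the SAP departs from the protocol without saying so.** Protocol 8.5 states its definition as a general one and leaves specific baselines to the SAP, so the silence of SAP 2.6 on this point carries little weight.
- **That a formal comparison of the arms is biased.** SAP 17 plans no statistical comparison of safety data, and the rule is the same in both arms.

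Each of these limits stands. None of them corrects the vital-sign change, shift and abnormality tables.

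**Conclusion.** The point holds in a limited form. As written, SAP 5.2 gives a post-dose vital-sign baseline on Day 1. If it is programmed that way:

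- the Day 1 end-of-infusion change is zero by construction for every treated patient with that reading (planned, about 308);
- first-infusion abnormalities are counted as baseline abnormalities or, at a boundary value such as 90 mmHg, drop out of both rows of Table 3;
- all later vital-sign changes start from a post-dose value.

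This assumes the literal reading of the same-day sentence. How many patients would be reclassified cannot be estimated from the documents, because the blood pressures used above are invented. The primary endpoint, PK, PD, laboratory and adverse-event analyses are not touched. The SAP should be corrected because a stated rule gives the wrong result in outputs that bear on an event of special interest, and the correct reading is already collected.

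**What to change.** 1. **SAP 5.2.** Define baseline as the last non-missing value before the date and time at which the first infusion starts. For vital signs this is the Day 1 pre-infusion reading or, if that is missing, the latest earlier value.
2. **SAP 5.2.** Keep the same-day rule only for assessments that have no recorded time or named time point and are scheduled pre-dose.
3. **SAP 17.5.** State that the Day 1 start-of-infusion and end-of-infusion readings count as post-baseline in the change, shift and abnormality outputs. This is needed because Protocol Table 1 labels Day 1 as the baseline visit and the SAP outputs refer to post-baseline visits, so a new definition alone might leave those readings out.
4. **SAP 2.6 (optional).** Note the definition there. Protocol 8.5 already allows the SAP to set specific baselines.

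The cost is a few sentences in the SAP, some programming, and a check of the vital-sign table shells. No new data are needed.

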## 5.3. RETESTS AND UNSCHEDULED VISITS DATA

Generally, data recorded at the nominal visit will be presented for by-visit summaries.

Unscheduled measurements will not be included in by-visit summaries, but will contribute to the best/worst case value where required (e.g. shift table).

In the case of a retest (same visit number assigned), the latest available measurement of non-PK/PD assessments for that visit will be used for by-visit summaries.

If the patient discontinued treatment during the study after Day 1 and the next visit data is missing, then early termination data, i.e. early treatment discontinuation visit data, will be mapped to the next available visit number for by-visit summaries. Otherwise, early termination data will not be mapped.

Listings will include scheduled, phone visit, unscheduled, retest and early study discontinuation data in chronological order. Listings will include all scheduled, unscheduled, retest, early discontinuation and phone visit data.

## 5.4. STATISTICAL TESTS

The default significant level will be 0.05 for statistical tests; the two-sided 95% CIs will be calculated, unless if specified otherwise.

---

Document:

Author:

Version Number:

Version Date:

Final v1.0

10Sep2019

Template No: CS\_TP\_BS016 Revision 4

Effective Date: 01Apr2016

Reference: CS\_WI\_BS005

## 5.5. COMMON CALCULATIONS

For quantitative measurements, change from Baseline at Visit X will be calculated as:

Change at Visit X= Test Value at Visit X – Baseline Value

The time from Date of Event A to Date of Event B (years) is calculated as:

- $(\text{Date of Event B} - \text{Date of Event A} + 1)/365.25$ .

The time from Date of Event A to Date of Event B (months) is calculated as:

- $(\text{Date of Event B} - \text{Date of Event A} + 1)/30.4375$ .

## 5.6. SOFTWARE VERSION

All derivations (except PK and PD parameter calculations), statistical analyses, summaries and listings will be generated using SAS® Version 9.4 or higher.

Pharmacokinetic and PD parameters will be calculated by non-compartmental model using Phoenix WinNonlin® 6.4 or higher (Pharsight Corporation, a Certara Company, Princeton, New Jersey), and/or SAS® Version 9.4 or higher (SAS Institute, Inc., Cary, North Carolina). Graphics may be prepared using the same versions of SAS®, or Phoenix WinNonlin®, or with SigmaPlot® 12.5, or higher (Systat Software, Inc., San Jose, California).

## 6. Statistical Considerations

### 6.1. MULTICENTER STUDIES

This study will be conducted by multiple investigators at multiple centers internationally.

Center pooling will be carried out across all centers for use in statistical summaries for this study.

### 6.2. MISSING DATA

Partial date will be imputed for the identification of treatment-emergent adverse events (TEAEs), prior/concomitant medication, calculation of demographic information and

---

Document:

Author:

Version Number:

Version Date:

Final v1.0

10Sep2019

Template No: CS\_TP\_BS016 Revision 4

Effective Date: 01Apr2016

Reference: CS\_WI\_BS005

medical history. Rules will be discussed in Appendix 1 of this SAP.

Main efficacy data will be handled in Section 15.1.2 and 15.2.2 of this SAP.

Missing PK concentrations will be handled as described in Section 13.

Unless otherwise specified, missing data will not be imputed in this study.

### **6.3. MULTIPLE COMPARISONS/ MULTIPLICITY**

No multiple comparison adjustment for any pharmacokinetic inferential analyses is planned since the significance level is specified by the regulators, and therefore the power calculations account for the two comparisons planned. No multiple comparison adjustment will be used for primary efficacy analysis, since there is only one primary efficacy analysis for Overall Response Rate (ORR) at Week 28.

### **6.4. DATA EXTRACTION RULE**

For the Week 28 CSR, only data up to the target visit will be included for reporting purpose. For example, at the Week 28 CSR, the cut-off date will be each patient's last assessment date at the Week 28 visit (or date of withdrawal if withdrawn before Week 28) or CT scans within 14 days, whichever comes last. For example, if one patient had CT scans 10 days after their Week 28 visit, his/her cut-off date will be the date of Week 28 visit+10; if a patient didn't have CT scans within 14 days of their Week 28 visit, his/her cut-off date will be the last assessment date of the Week 28 visit. The cut-off date for each patient may be different. Specific data extraction rules are described in Appendix 2.

## **7. Output Presentations**

The TLF templates provided with this SAP describe the conventions for the presentation of data in outputs, and the format and content of the summary tables, figures and listings.

Some minor modifications may be necessary to the planned design of tables, figures, and listings to accommodate data collected during the actual study conduct.

## **8. Disposition and Withdrawals**

The number of patients who were screened (enrolled) will be presented. Patient disposition and withdrawals will be presented by treatment group and overall. The number

---

Document:

Author:

Version Number:

Version Date:

Final v1.0

10Sep2019

Template No: CS\_TP\_BS016 Revision 4

Effective Date: 01Apr2016

Reference: CS\_WI\_BS005

and percentage of patients who were randomized, who were randomized in error, who were treated and who were not treated, who completed the study, discontinued study drug with reason for discontinuation, and withdrew early from the study by reason for withdrawal will be presented.

Protocol deviations (as defined in section 4.8) will be presented by treatment group for the RAN.

Number (%) of patients in the analysis sets and excluded from each analysis set will be summarized by treatment group and reason for the RAN.

## 9. Demographic and other Baseline Characteristics

Patient demographics and baseline characteristics will be summarized by treatment group and overall for the RAN and FAS. If the FAS is the same as the RAN, then only the RAN will be summarized. Continuous variables will be summarized with descriptive statistics (n, mean, SD, median, minimum and maximum). Categorical variables will be summarized with counts and percentages.

The following demographics and baseline characteristics will be summarized appropriately for the study:

### Demographics

- Age (years) – calculated to date of Informed Consent
- Age group – 18-60 years, >60 years
- Gender – Female, Male
- Ethnicity– Hispanic or Latino, Not Hispanic or Latino, Not Reported, Unknown
- Race – American Indian or Alaska Native, Asian, Black or African American, Native Hawaiian or other Pacific Islander, White, Other, Unknown, Not Reported
- Weight (kg) at Baseline
- Height (cm) at Baseline
- Body Mass Index (BMI) ( $\text{kg}/\text{m}^2$ ) – derived as  $\text{weight (kg)}/(\text{height (m)})^2$
- Body Surface Area (BSA) ( $\text{m}^2$ ) – Collected from eCRF, derived using the Du Bios

---

Document:

Author:

Version Number:

Final v1.0

Version Date:

10Sep2019

Template No: CS\_TP\_BS016 Revision 4

Reference: CS\_WI\_BS005

Effective Date: 01Apr2016

formula, given as  $BSA = 0.20247 \times \text{height (m)}^{0.725} \times \text{weight (kg)}^{0.425}$

Baseline Characteristics

- Disease duration (years) – calculated the first diagnosis date of LTBFL relative to date of informed consent
- Childbearing potential – Yes, No
- Risk groups according to FLIPI-2 score – Low risk, Intermediate risk, High risk

The FLIPI-2 includes five adverse prognostic factors as below, and risk groups will be graded with presenting a number of risk factors (from 0 to 5).

Parameter	Adverse Factors
Age	>60 years
Hemoglobin level	<120 g/L
β2-microglobulin level	Above upper limit of normal
Longest diameter of largest involved node	>6 cm
Bone marrow involvement	Present

Risk Group	Number of Adverse Factors
Low risk	0-1
Intermediate risk	2
High risk	3-5

- ECOG performance status – 0, 1
- Ann Arbor Stage – I, II, III, IV with appropriate modifier appended if available (e.g., IE)
- Type of Ann Arbor Staging – CS, PS
- Histological confirmation of LTBFL diagnosis information will be listed
- Anti-drug antibody (ADA) status at baseline (positive, negative)

Document:

Author:

Version Number:

Version Date:

Final v1.0

10Sep2019

Template No: CS\_TP\_BS016 Revision 4

Effective Date: 01Apr2016

Reference: CS\_WI\_BS005

